## **2.4 Study Population**

We will include individuals who:

- Provide informed consent and sign a HIPPA form prior to any study procedures are performed.
- Have completed all other formal physical therapy and therapeutic exercise regimens, and will not be engaging in any other formal therapy for their ACLR during the study
- Are between the ages of 18 and 35.
- Underwent an ACLR no earlier than 6 months and no later than 5 years prior to enrollment.
- Demonstrate < 8,000 steps per day during the screening phase of the study as assessed using the Actigraph GT9X Link monitor
- Demonstrate clinically relevant-knee symptoms, defined as a KOOS-QOL subscale score < 72.2.  
This criteria was updated and approved by the IRB on 5/5/2022 to expand criteria to include individuals reporting KOOS QOL score <87.52.

Participants will be excluded if:

- The participant underwent an ACLR revision surgery due to a previous ACL graft injury
- Multiple ligament surgery was indicated at the time of ACLR surgery.
- A lower extremity fracture was suffered during the ACL injury.
- The participant has been diagnosed with osteoarthritis in either knee.

Due to the MRI outcomes participants will be excluded if they have:

- Cochlear implant
- Metal in body
- Claustrophobia
- History of seizures

## 3 STUDY PROCEDURES

### 3.1 Screening Procedures

Once a potential participant has been identified and has indicated that he/she is interested in participating in the study, a study team member will then administer a screening questionnaire via telephone or in person at the orthopaedic clinic or the laboratory to further assess eligibility. We will obtain participants' verbal consent to ask a limited number of questions that include inclusion/exclusion criteria. If the individual meets self-reported screening criteria, score less than 87.5 on the KOOS quality of life subscale, and are interested in participating, participants will provide written informed consent and sign a HIPPA form at the clinic. They will be outfitted with a research-grade actigraph accelerometer to monitor daily during free-living settings for 7 days and fill out the demographic form, knee injury history form. The actigraph will be secured on a belt and placed on the right hip. Participants will be instructed to wear the device for 7 days (removed for water activity and sleep). After 7 days, participants will return to the laboratory. If participants average <8000 steps per day over the wear period then they will continue with the baseline visit.

### 3.2 Baseline Visit Procedures

If participants average <8000 steps per day over the wear period then they will undergo an MRI at the Biomedical Imaging Research Center, complete surveys (KOOS) and be outfitted with a Fitbit Charge 2 monitor on their wrist by a researcher.

After this process is complete, participants will be connected to a member of the Michigan State University study team using a HIPAA compliant video conferencing platform. The investigator from MSU will guide the participant through monitor initialization and sync the monitor with the participant's personal mobile device. The Fitbit Versa 2 is well suited for our study design based on its ability to display SMS messages on a digital interface, ease of charging, ability to wirelessly sync data using a smartphone, and ability to continuously capture daily steps using the Fitbit Application Programming Interface (API). Monitor will be worn during all waking hours, and compliance will be considered as a day with = 1,000 steps recorded. At this visit participants will be provided a handout that describes the physical activity promotion exposure, dates of the physical activity promotion (8 weeks), and a reminder card indicating the date of their follow-up visit.

### **3.3 Intervention/Treatment procedures**

Detailed procedures can be found in "Appendix A. Extended Intervention Document." Following monitor initialization and registration, participants will complete a 14-day "run-in" period during which they will wear the Fitbit (=10 days of compliance) but no physical activity promotion will occur. This establishes participant compliance, understanding of the Fitbit, and baseline daily step data to generate the first individualized step goals for the physical activity promotion period. Individuals who do not meet compliance requirements needed to set the daily goals (>10 days with at least 1,000 steps). Participants who are compliant will be exposed to physical activity promotion for 8 weeks. During this period of time, participants will receive an SMS message (or email if they don't have a smart phone) each morning containing a personalized step count goal for the day and a link which they will click to confirm receipt of the goal. To set the daily goal, the preceding 10 days of step data will be rank ordered and 60th percentile step count will be set as the goal for the following day. Calculation of daily goals will be automated, and will occur prior to our standard goal communication time (8 AM).

### **3.4 Follow-up procedures**

After the intervention, participants will be outfitted at the laboratory with the research-grade actigraph accelerometer to monitor daily during free-living settings for 7 days and fill out the surveys (KOOS). The actigraph will be secured on a belt and placed on the right hip. Participants will be instructed to wear the device for 7 days (removed for water activity and sleep). Participants will also undergo another MRI of the surgical limb at the Biomedical Imaging Research Center.

### **3.5 Unscheduled visits – N/A**

### **3.6 Concomitant Medication documentation – N/A**

### **3.7 Rescue medication administration (if applicable) – N/A**

### **3.8 Subject Completion/ Withdrawal procedures**

A participant may be withdrawn from the study at any time if the participant or the investigator feels that it is not in the subject's best interest to continue. All participants are free to withdraw from participation at any time, for any reason, specified or unspecified, and without prejudice. A participant will be withdrawn from the study for non-compliance of the protocol or lost to follow-up. Reasonable attempts will be made by the investigator to provide a reason for subject withdrawals.

### **3.9 Screen failure procedures:**

A participant will screen out from the study if:

- 1) They don't meet screening criteria (<8000 steps per day over 7 days during the initial actigraph physical activity monitoring period)
- 2) They are non-compliant with the Fitbit monitoring "run in" observation period over 14 days. A participant will be determined non-compliant if they fail to accumulate 1,000 daily steps for more than 5 days during this period of time.

Participants will be notified that they failed the screening to qualify for the intervention, return the actigraph or fitbit monitor, and not continue with the baseline visit, intervention, or follow-up visit.

## **4 STUDY EVALUATIONS AND MEASUREMENTS**

### **4.1 Efficacy Evaluation (if applicable)**

Cartilage Composition: Cartilage composition will be measured using T1p relaxation times (ms) of medial and lateral tibiofemoral articular cartilage from MRI imaging. The measurement demonstrates excellent test-retest and inter-rater reliability. T1p relaxation times are inversely related to cartilage proteoglycan density. Lower T1p relaxation times or decreases in T1p relaxation times indicate greater proteoglycan density or increase proteoglycan density respectively.

Daily Steps: Objective daily step counts measured via Triaxial accelerometer and averaged over 7 days or wear (i.e., Actigraph Link or Fitbit Charge 2)

Self-Reported Knee Function: The Knee Injury and Osteoarthritis Outcomes Score (KOOS) Questionnaire assesses the participant's opinion about their pain, other symptoms, function in activities of daily living, function in sport and recreation and knee related quality of life. We will focus the primary analysis on the KOOS-QOL subscale, as it represents the most responsive KOOS subscale. The KOOS is a valid and reliable self-reported questionnaire of outcomes following knee specific injury and has been used previously by the PI. All other KOOS subscales will be collected and analyzed alternative analyses. KOOS QOL is measured on a scale of 0-100 with a greater score indicating better self-reported knee function.

Feasibility Outcomes: intervention retention rates (%) and intervention compliance (%)

### **4.2 Pharmacokinetic Evaluation (if applicable) - N/A**

#### 4.3 Safety Evaluations

##### Medical Monitor:

All adverse events will be reported to [name] from the MOTION Science Institute at the University of North Carolina at Chapel Hill (UNC-CH). [name], Co-Director of the (MusculOskeleTal Injury preventiON) MOTION Science Institute, will be responsible for the independent safety monitoring since he is not a co-investigator or collaborator on this project. [name] has previous experience as a PI in clinical trials for patients with knee injuries (NCT02605876) and therefore has the experience and knowledge regarding the scientific area of study and study design, which will be important in understanding the analysis and interpretation of the data to ensure participant safety as well as ethical, scientifically rigorous study conduct.

##### Institutional Review Board

The research described in this proposal meets the definition of human subject's research of a biomedical or behavioral nature. As such, we have approval from human subjects research from the IRB for Biomedical Research at UNC-CH. This approval has been obtained prior to the recruitment or enrollment of study participants and the collection of any study-related data. The Michigan State University (MSU) study team and IRB for Biomedical Research will rely on the UNC-CH IRB for Biomedical Research as the single IRB for the duration of the proposed study.

##### Routine Safety Reports and Expedited Safety Reports

[name] or [name] will report all adverse events (both serious and non-serious), unanticipated problems, study progress, and protocol deviations to the safety officer, [name] (who is not affiliated with the study), on a biannual basis (every 6 months) or as requested in a detail and summary format. All adverse events (both non-serious and serious) will be collected, analyzed, and monitored in the study's adverse event log, which is kept in [name] and [name] regulatory files on a secured server. [name] will also ensure the enrollment rate is consistent with the project timeline, verify that the participants meet enrollment criteria, and that each subject has been consented. Please see Section 7: Safety Management for more details.

## STATISTICAL CONSIDERATIONS

#### 4.4 Primary Endpoint

- 1.) T1rho relaxation times in the medial femoral condyle at pre-intervention: MRI marker of T1rho relaxation times of medial femoral articular cartilage (i.e proteoglycan density) at pre-intervention
- 2.) T1rho relaxation times in the medial femoral condyle at post-intervention: MRI marker of T1rho relaxation times of medial femoral articular cartilage (i.e proteoglycan density) at post-intervention
- 3.) T1rho relaxation times in the lateral femoral condyle at pre-intervention: MRI marker of T1rho relaxation times of lateral femoral articular cartilage (i.e proteoglycan density) at pre-intervention
- 4.) T1rho relaxation times in the lateral femoral condyle at post-intervention: MRI marker of T1rho relaxation times of lateral femoral articular cartilage (i.e proteoglycan density) at post-intervention

- 5.) T1rho relaxation times in the medial tibial condyle at pre-intervention: MRI marker of T1rho relaxation times of medial tibial articular cartilage (i.e proteoglycan density) at pre-intervention
- 6.) T1rho relaxation times in the medial tibial condyle at post-intervention: MRI marker of T1rho relaxation times of medial tibial articular cartilage (i.e proteoglycan density) at post-intervention
- 7.) T1rho relaxation times in the lateral tibial condyle at pre-intervention: MRI marker of T1rho relaxation times of lateral tibial articular cartilage (i.e proteoglycan density) at pre-intervention
- 8.) T1rho relaxation times in the lateral tibial at post-intervention: MRI marker of T1rho relaxation times of lateral tibial articular cartilage (i.e proteoglycan density) at post-intervention
- 9.) Change in daily steps: change in average steps per day over 7 day physical activity monitor wear pre-intervention (baseline) to approximately 8-weeks (post-intervention) after physical activity promotion intervention
- 10.) Change in T1rho relaxation times in the medial femoral condyle: change in MRI marker of T1rho relaxation times of medial femoral articular cartilage (i.e proteoglycan density) from pre-intervention (baseline) to approximately 8-weeks (post-intervention) after physical activity promotion intervention
- 11.) Change in T1rho relaxation times in the medial tibial condyle: change in MRI marker of T1rho relaxation times of medial tibial articular cartilage (i.e proteoglycan density) from pre-intervention (baseline) to approximately 8-weeks (post-intervention) after physical activity promotion intervention
- 12.) Change in T1rho relaxation times in the lateral femoral condyle: change in MRI marker of T1rho relaxation times of lateral femoral articular cartilage (i.e proteoglycan density) from pre-intervention (baseline) to approximately 8-weeks (post-intervention) after physical activity promotion intervention
- 13.) Change in T1rho relaxation times in the lateral tibial condyle: change in MRI marker of T1rho relaxation times of lateral tibial articular cartilage (i.e proteoglycan density) from pre-intervention (baseline) to approximately 8-weeks (post-intervention) after physical activity promotion intervention

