## 2 INVESTIGATIONAL PLAN (brief overview)

### 2.1 Study Design

Type of design: Single-arm pre-test post-test clinical trial

- Screening Visit: The initial visit will include initial screening (i.e. screening question and fill out KOOS-QOL subscale), enrollment, walking biomechanics assessment, and instructional use of actigraph physical activity monitor which will be worn for 7 days during all waking hours.
- Baseline: The second visit will include Fitbit and smartphone initialization with MSU Researcher, collection of patient reported outcomes and MRI scan of their knee. Participants will wear the fitbit monitor on their non-dominant wrist for 2 weeks during all waking hours in free-living settings in preparation for the intervention.
- Intervention/Treatment: Between the second and third visit, participants will receive daily SMS message with daily step count goals on their smart phone for 8 weeks. The daily step goal is based

on an adaptive step goal paradigm in which their daily goal is based on the top 60th percentile of steps over the last 10 days.

- Follow up: The third visit will include the completion of surveys, returning the fitbit monitor, instructional use of the actigraph monitor for second wear period over 7 days, and MRI.

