#### **4.5 Secondary Endpoint**

- 1.) KOOS-QOL subscale at pre-intervention
- 2.) KOOS-QOL subscale at post-intervention
- 3.) Daily step promotion intervention retention: percentage of patients retained at post-intervention visit
- 4.) Daily step promotion intervention compliance: percentage of days participant is compliant with fitbit monitor wear (>1,000 steps per day)

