## 8. DATA COLLECTION AND MANAGEMENT

All data storing and sharing methods will be approved by the UNC-CH's Institutional Review Board.

In Person Study Data Protections: Prior to performing any study related activities, potential adult participants will provide written informed consent. All consent procedures will be completed by qualified and trained members of the study team. This includes informing each potential participant of the purpose of the project, possible risks, their personal rights, and potential benefits of the study. All possible exclusion criteria will be verified following informed consent. Extreme care will be taken to ensure that there will be no breach of participant confidentiality.

Outcomes Data: All outcomes data will be managed using REDCap, which is a secure online platform for building and managing online databases provided at no cost to investigators at UNC-CH. The study team has been using REDCap for the past 5 years and is versed in building, acquiring and securing data using this database. REDCap also provides automated export to statistical packages (e.g. R, SPSS, and SAS) that will be used to analyze data from this study. UNC-CH also offers REDCap training twice a month as well as onsite support for assistance in building or managing REDCap databases. All pre-processed and post-processed Actigraph physical activity data, magnetic resonance imaging data, patient-reported outcome data will be stored electronically on a secure password-protected server maintained by UNC-CH. Only investigators with IRB and PI clearance will be given access to the password-protected folders on the secure server. All individuals must have current UNC-CH online access credentials to access the server and personal access will be reviewed annually to purge or renew personnel access. The PI can remove access to the server for individuals if necessary.

- Data Entry: data will be entered into REDCap from electronic files by investigators (i.e. processed magnetic resonance imaging data and joint tissue metabolism) or directly by study participants (i.e. demographics, patient-reported outcomes). Outcome measures will be cut and pasted from electronic files or collection software into REDCap to minimize data entry error. All outcome measure data will be entered by two individual investigators.

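### Endpoint 9 names no device or weeks; read as Actigraph, its baseline is the week that selected participants for low steps, so the single-arm mean gain includes regression to the mean

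*Combined protocol and SAP*

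**What the plan says.** Section 4.4 lists as primary endpoint 9 the "change in average steps per day over 7 day physical activity monitor wear pre-intervention (baseline) to approximately 8-weeks (post-intervention". Section 4.1 describes daily steps as "averaged over 7 days or wear (i.e., Actigraph Link or Fitbit Charge 2", which does not choose between the devices.

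The rest of the protocol points to the Actigraph:

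- The only scheduled 7-day wears are Actigraph wears, one at screening (sections 2.3 and 3.1) and one at follow-up: "After the intervention, participants will be outfitted at the laboratory with the research-grade actigraph accelerometer to monitor daily during free-living settings for 7 days" (section 3.4).
- Section 2.1 describes the third visit as including "returning the fitbit monitor, instructional use of the actigraph monitor for second wear period over 7 days, and MRI", so the follow-up week is the second Actigraph period.
- Section 8, under outcomes data, says "All pre-processed and post-processed Actigraph physical activity data, magnetic resonance imaging data, patient-reported outcome data will be stored electronically".

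The screening week is also the entry test: "If participants average <8000 steps per day over the wear period then they will continue with the baseline visit" (section 3.1).

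The Fitbit is worn from the baseline visit through the run-in and the 8 intervention weeks. Its data have these stated uses: run-in compliance and "baseline daily step data to generate the first individualized step goals for the physical activity promotion period" (section 3.3); the compliance endpoint, "percentage of days participant is compliant with fitbit monitor wear (>1,000 steps per day" (section 4.5); and usage and adherence tracking (Appendix A). Aim 2 relates change in steps to change in T1rho and names no device.

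**The concern.** Two things follow from the Actigraph reading, and the plan comments on neither.

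First, a person whose screening week happened to be low is more likely to be admitted. The same low week is then subtracted from the follow-up week, so some gain is expected even if nobody changes behaviour. With one arm, nothing in the data separates this from an effect of the step goals. Section 4.6 says the estimates are meant for future grant proposals, so an uncaveated gain would be carried forward.

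Second, Aim 2 asks whether change in loading goes with change in cartilage between the scans, but neither Actigraph week falls between them. The follow-up week starts after the goals end, so it reflects loading during the intervention only as far as gains persist, and the documents give no persistence figure. The steps recorded between the scans are on the Fitbit.

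**Working it through.** **The plan's own figure.** Section 4.7 gives no SD, reliability or expected gain for steps. Its only figure that involves endpoint 9 is a detectable correlation of 0.77 with 8 completers at 80% power, two-sided 0.05. With a noncentral t and a fixed predictor, the noncentrality is 0.77/√(1 − 0.77²) × √8 = 3.41 on 6 df, and power is 81.0%. The figure reproduces on that model. It says nothing about the mean gain.

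**Timeline (nominal).**

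| Event | Day |
|---|---|
| Actigraph screening week | 0 to 7 |
| Baseline visit with MRI 1, Fitbit starts | 7 |
| Run-in (14 days in section 3.3) | 7 to 21 |
| Intervention (56 days) | 21 to 77 |
| Third visit with MRI 2, Fitbit returned | 77 |
| Actigraph follow-up week | 77 to 84 |

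The scans are 14 + 56 = 70 days apart. The Actigraph weeks start 7 + 14 + 56 = 77 days apart and bracket the scans.

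**Regression to the mean.** Let a person's 7-day mean be normal with standard deviation SD in the screened population, and let ICC be the week-to-week correlation. With no true change, the expected gain after selecting on a mean below 8,000 is

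(1 − ICC) × (mean of all screened − mean of those selected) = (1 − ICC) × SD × φ(c)/Φ(c),

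where Φ(c) is the share below 8,000.

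- From the documents: the share is about 50% at 6 to 12 months (section 1.4, Relevant Literature and Data) and two thirds up to 5 years (section 2.3). Then φ(c)/Φ(c) is 0.798 and 0.545.
- Assumed, because the documents give neither: SD 2,500 to 3,000 and ICC 0.7 to 0.9.

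| Share below 8,000 | SD | Mean, all | Mean, selected | Spurious gain, ICC 0.9 | Spurious gain, ICC 0.7 |
|---|---|---|---|---|---|
| 50% | 2,500 | 8,000 | 6,005 | 199 | 598 |
| 50% | 3,000 | 8,000 | 5,606 | 239 | 718 |
| 67% | 2,500 | 6,923 | 5,560 | 136 | 409 |
| 67% | 3,000 | 6,708 | 5,072 | 164 | 491 |

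The range is 136 to 718 steps per day. Against the roughly 2,000-step gain cited in section 1.4, that is 136/2,000 = 7% to 718/2,000 = 36%. Wider assumptions (SD 2,000 to 3,500, ICC 0.6 to 0.9) give 109 to 1,117, or about 5% to 56%. A simulation with no true change (two thirds below 8,000, SD 2,500, ICC 0.8) gave 272 against 273 from the formula.

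**A baseline that did not select on steps.** In the same simulation, a separate baseline with independent error left a spurious gain of 0.8 steps per day. If screening and run-in errors have equal SD and correlate at 0.2 (assumed), the remainder is 0.2 × 136 = 27 to 0.2 × 718 = 144.

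**What this does to Aim 2.** The expected spurious gain differs between people: it is (1 − ICC) × (population mean − own baseline). At ICC 0.7 and mean 8,000 it is 0.3 × 500 = 150 for a baseline of 7,500 and 0.3 × 4,000 = 1,200 for a baseline of 4,000. Unless the chance error in the screening week is related to T1rho change, it acts mainly as noise in the step change and pulls r towards zero.

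**The case against.** The strongest reply is that the plan hardly uses the mean step gain. No aim or hypothesis tests it, steps enter only Aim 2, and the synopsis ties Cohen's d to the MRI measures. That is correct and limits the weight of the point. Even so, the change in steps is a listed primary endpoint, and its mean is what shows whether the intervention raised steps at all.

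Four stronger readings are tempting, and the documents do not support them.

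- *The reported gain overstates the intervention's effect on balance.* The follow-up week comes after the goals end. If half of a 2,000-step gain had been lost by then, that is 1,000 steps in the other direction, more than the whole 140 to 720 range. The regression-to-the-mean component is upward, but the net error relative to the gain during the intervention is not established.
- *The Fitbit contrast is the better one and should replace the Actigraph change.* It averages more days, but which contrast tracks loading better depends on how fast gains build and how well they last. The documents give neither.
- *The plan excludes the Fitbit from Aim 2.* It does not. Section 4.1 names the Fitbit as a daily-step instrument; its data are simply not assigned.
- *The reuse of the screening week is concealed.* Sections 2.3, 3.1 and 3.9 state the step rule openly. Only the consequence for the mean gain is missing.

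It is also fair to say that sampling error dominates Aim 2. For an illustrative r of 0.50 with 8 participants, the Fisher interval is tanh(0.549 ± 1.96/√5) = −0.32 to 0.89. A supportive correlation would be just as imprecise. Its value is in fixing the choice of device and window beforehand.

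**Conclusion.** The point holds as a minor one. Endpoint 9 leaves the device and weeks open. On its natural reading the baseline is the selection week, so the mean gain has an upward regression-to-the-mean component that a single arm cannot separate from an effect. The direction needs only a week-to-week correlation below 1. The size, about 140 to 720 steps per day, rests on an assumed SD and ICC and on a normal model, and should be quoted only with those assumptions.

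For Aim 2 the consequence is added noise and a mismatch between when steps are measured and when cartilage is imaged. It does not show that the planned correlation is invalid.

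**What to change.** In a dated amendment before analysis:

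1. State in endpoint 9 that the change is the Actigraph follow-up week minus the Actigraph screening week, and state in section 4.1 that devices are never mixed within a change score.
2. Report the mean gain a second way: mean Fitbit steps on valid intervention days minus mean Fitbit steps on valid run-in days. The run-in was not used for the under-8,000 criterion, although it does screen for wear compliance. State in the report that the Actigraph gain includes regression to the mean.
3. Add one pre-specified supportive Aim 2 analysis correlating that Fitbit change with T1rho change in the four regions. It does not replace the Actigraph change.

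No new data are collected. The costs are:

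- four more correlations at n = 8, so four become eight;
- reliance on a consumer wrist device and on a 1,000-step wear rule that admits partly worn days;
- possible reactivity to wearing the device in the run-in, which would understate the Fitbit gain;
- a run-in that falls after MRI 1;
- two gains that differ by device and window, so their difference is not a clean estimate of regression to the mean.

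Two separate inconsistencies should be reconciled at the same time because the Fitbit contrast depends on them. The run-in is 14 days in sections 1.2 and 3.3 but 10 days in the Appendix A syncing instructions. The Fitbit is a Charge 2 in most places, but section 3.2 names both Charge 2 and Versa 2, and section 8 names Versa 2.
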